8.2 Definitions

Definitions of AEs, adverse drug reactions, SAEs, serious, unexpected adverse drug reactions (SUSARs), and AEs of special interest (AESI) are presented below.

AE: An AE is defined as the appearance of (or worsening of pre-existing) an undesirable sign, symptom, or medical condition that occurs after patient's signed ICF has been obtained. Abnormal laboratory values or test results occurring after informed consent constitute AEs only if they induce clinical signs or symptoms, are considered clinically significant, require therapy (eg, hematologic abnormality that requires transfusion or hematological stem cell support), or require changes in study medication.

Adverse drug reaction: An adverse drug reaction is an unwanted or harmful reaction that occurs after administration of a drug or drugs and is suspected or known to be due to the drug. Adverse drug reactions have traditionally been categorized as pharmacologic (predicted based on the pharmacology of the drug) or idiosyncratic (not predicted based on pharmacology).

SAE: A SAE is any AE that meets any of the following criteria:

- Is fatal or life-threatening
- Results in persistent or significant disability or incapacity
- Constitutes a congenital anomaly/birth defect
- Is medically significant, ie, defined as an event that jeopardizes the patient or may require medical or surgical intervention to prevent the outcomes listed above
- Requires in-patient hospitalization or prolongation of existing hospitalization, unless hospitalization is for the following:
 - Routine treatment or monitoring of the studied indication not associated with any deterioration in condition
 - Elective or pre-planned treatment for a pre-existing condition that is unrelated to the indication under study and has not worsened since signing the informed consent
 - Treatment on an emergency out-patient basis for an event not fulfilling any of the definitions of a SAE given above and not resulting in hospital admission
 - Social reasons and respite care in the absence of any deterioration in the patient's general condition

Unexpected adverse drug reaction: An adverse drug reaction that is not consistent with applicable product information or characteristics of the study drug.

Suspected, unexpected, serious adverse reaction (SUSAR): A SUSAR is an adverse reaction meeting serious criteria (above), the nature or severity of which is not consistent with the reference safety information for the investigational drug(s).

Adverse events of special interest (AESI): An AESI (serious or non-serious) is an AE with scientific and/or medical concern specific to the Sponsor's program, for which ongoing monitoring and rapid communication by the Investigator to the Sponsor can be appropriate. CRS is considered as an AESI for IMCnyeso. Refer to the IMCnyeso Investigator's Brochure for details on the AESI for IMCnyeso.

8.3 Criteria for Expectedness

The concept of expectedness refers to events that may or may not have previously been observed and documented and not necessarily the known pharmacological properties of the medicine. An AE will be unexpected for purposes of regulatory reporting unless it is mentioned in the

appropriate reference safety information within the current Investigator's Brochure for the investigational drug, even if it is a medical occurrence expected for the disease being treated.

8.4 Assessment of Causality

The Investigator decides whether he or she interprets the observed AE as either related to disease, to the study medication, study procedure, or other concomitant treatment or pathologies. To assess the relationship of the AE to the study drug, the following terms are defined:

- **Related:** A direct cause and effect relationship between the study treatment and the AE is likely
- **Possibly related:** A cause and effect relationship between the study treatment and the AE has not been demonstrated at this time and is not probable, but is also not impossible
- **Not related:** Without question, the AE is definitely not associated with the study treatment

All "related" and "possibly related" AEs and SAEs will be defined as related to study drug.

8.5 Adverse Event Reporting

The Investigator must notify the Sponsor within 24 hours of any SAE, DLT, \geq Grade 2 CRS, or \geq Grade 3 hepatic function abnormality.

8.5.1 Expedited Reporting

Cases of adverse drug reactions from all sources that are assessed as serious are subject to expedited reporting. Expedited reporting of cases will comply with country-specific regulatory requirements relating to safety reporting to the regulatory authority, IRB/IEC and Investigators. Additionally, any safety information from other observations that could change the benefit-risk evaluation of the product will be communicated in an expedited manner to the regulatory authorities and all Investigators by the Sponsor.

The CRO will be responsible for the processing and reporting of SAEs. AEs will be coded by using International Conference on Harmonisation (ICH) Medical Dictionary for Regulatory Activities.

Minimum criteria for a valid adverse drug reaction case have been established by ICH and individual regulatory agencies and are listed as the following:

- An identifiable reporter

- An identifiable patient
- A reaction/event
- A suspected medicinal product
- Other safety issues that also qualify for expedited reporting by the Sponsor are those that would materially alter the current benefit-risk assessment of the investigational product (sufficient to consider changes in the administration or in the overall conduct of the trial). Although these events will not be reported as SUSARs, they might require other action, such as putting in place urgent safety measures, the generation of substantial amendments, or early termination of the trial. The Sponsor will inform the regulatory authorities and all IEC of safety issues that might materially alter the benefit-risk assessment of the investigational agents.

8.5.2 Standards for Expedited Reporting

Cases of adverse drug reactions from all sources that are assessed as suspected, unexpected and serious (SUSAR) are subject to expedited reporting. Additionally, any safety information from other observations that could change the benefit-risk evaluation of the product should be promptly communicated to the regulatory authorities. Any other SUSARs associated with the investigational product should be reported as soon as the Sponsor becomes aware of them. This includes SUSARs that occur in another trial conducted by the same Sponsor, are identified by spontaneous reports or a publication, or are transmitted to the Sponsor by another regulatory authority.

8.5.3 Reporting of Out-of-Range Laboratory Test Results as Adverse Events

Out-of-range laboratory test results should be reported as AEs if, in the opinion of the Principal Investigator, they are clinically significant. Abnormal laboratory results that are not considered to be clinically significant will not be reported as AEs. Significance of abnormal laboratory results should be documented in the study records.

When an abnormal laboratory value is recorded as an AE, the diagnosis (eg, anemia) should be recorded as the event term, not the abnormality (eg, low hemoglobin or hemoglobin decreased).

8.5.4 Reporting Events Associated with Disease Progression

Clinically significant signs or symptoms that occur due to disease progression should be reported as AE/SAE. However, to avoid inconsistencies in the clinical database, neither the term “disease progression” nor identification of a new lesion should be reported as an AE/SAE. Instead, information about disease progression, including any new lesions, is to be reported on the disease assessment pages. Similarly, death due to progression of the malignancy under study should not

be reported as a fatal SAE, and information about the cause of death is to be reported on the death eCRF page.

8.5.5 Reporting Guidelines for Other Observations

Other safety issues that qualify for expedited reporting where they might materially alter the current benefit-risk assessment of the investigational product (sufficient to consider changes in the administration or in the overall conduct of the trial) include:

- An increase in the rate of occurrence of an expected serious adverse reaction, which is judged to be clinically important
- A post-study SUSAR that occurs after the patient has completed a clinical trial and is reported by the Investigator to the Sponsor

Events that occur during the trial and are relevant in terms of patient safety, but do not fall within the definition of SUSAR (therefore are not subject to the reporting requirements for SUSARs) are:

- A SAE that could be associated with the trial procedures and could modify the conduct of the trial
- A significant hazard to the patient population (eg, lack of efficacy of an investigational medicinal product)
- A major safety finding from a newly completed animal study (eg, carcinogenicity)
- A temporary halt of a trial for safety reasons if the trial is conducted with the same investigational medicinal product in another country by the same Sponsor
- Safety recommendations of the SST

Although these events/observations will not be reported as SUSARs, they might require other action, such as putting in place urgent safety measures, the generation of substantial amendments, or early termination of the trial. The Sponsor will inform the regulatory authorities and the IEC of safety issues that might materially alter the benefit-risk assessment of the investigational medicinal product.

Expedited reporting is not usually required for reactions that are serious but expected or for non-serious adverse reactions whether expected or not. It is also usually inappropriate to report events that are considered unrelated to the investigational medicinal product.

8.5.6 Pregnancy Reporting

Pregnancy will be reported through the Pregnancy Reporting Form (paper) and in the eCRF. The Pregnancy Reporting Form (paper) should be completed and reported as indicated to the CRO pharmacovigilance team within 24 hours of being made aware of the event. Women who become pregnant during the study will be withdrawn from treatment at the earliest opportunity. The CRO will then notify the Sponsor within 1-business day of being informed of the event. Following permanent discontinuation of study treatment, every attempt will be made to follow the patient and any resulting offspring for up to 6-weeks postpartum, unless otherwise medically indicated. Abortion, stillbirth, or any malformation/disease in the offspring must be reported as a SAE.

For men participating in the study who report the pregnancy of a partner, the Investigator will ask to collect information about the results of the pregnancy/birth using the Pregnant Partner Form. The partner may be asked to sign a consent form giving permission for information to be collected. This health information will become part of the research study records. It will be shared with the Sponsor.

8.6 Investigator's Responsibilities

The Investigator is responsible for the collection of AE data. All AEs must be recorded in the eCRF.

The Investigator must report all SAEs within 24 hours of being made aware of the event to pharmacovigilance via the clinical database by completing as much information about the AE as possible in the eCRF and checking “Yes” on the “Serious?” checkbox. The initial reporting can be supplemented by written reports using the SAE report form provided.

If the eCRF is unavailable, or paper reports are to be submitted, forms should be faxed to the CRO pharmacovigilance team using the safety hotline number:

- Safety Hotline (Fax): [REDACTED] (US and Canada), [REDACTED] (UK)

The following minimum information is required for the SAE report:

- Patient identification (patient number and age)
- Trial number
- Study therapy (dose, route, form, regime, start date, and end date)
- Concomitant medication (including dose, route, form, regimen, and start date where available)

- Nature of SAE (overall diagnosis where available or signs and symptoms)
- Date and time of occurrence
- Any associated factors (concomitant disease or medication)
- Proposed relationship to study therapy
- Outcome
- Identification of the reporter
- Action in relation to study (withdrawn from treatment, suspended, or none)

Investigators may be asked for additional information for any reported SAE, such as laboratory or diagnostic reports or the outcome of the event. A SAE follow-up report with attached documents (if necessary) should be forwarded to CRO pharmacovigilance as soon as the additional information is available by email. The study number IMCnyeso-101 must be in the title of any email for study identification purposes and the unique patient identification number must be referenced.

8.7 Sponsor and Clinical Research Organization's Responsibilities

The Sponsor is responsible for the ongoing safety evaluation of the investigational drugs being studied. The Sponsor and CRO are responsible for ensuring that expedited reports are made to all concerned Investigators, to the IEC where required, and to all regulatory authorities of all adverse drug reactions that are both serious and unexpected, findings that could adversely affect the health of patients, impact the conduct of the trial, or alter the competent authority's authorization to continue the trial in accordance with local applicable regulations.

9 STATISTICAL METHODS AND DATA ANALYSES

9.1 General Principles

Categorical data will be presented as frequencies and percentages. For continuous data, the mean, standard deviation, median, minimum and the maximum will be presented.

The Phase I study data will be analyzed and reported based on all patient data from the dose escalation up to the time when all Phase I patients have completed at least 6 cycles of treatment or have discontinued study treatment. Data will be listed, summarized, and analyzed by treatment group. Data for the Phase II expansion cohorts will be reported separately, with a data cut off at the point where at least 80% of patients have completed the follow up for disease progression or discontinued the study for any reason. Additional details of data reporting will be outlined in the statistical analysis plan (SAP).

The following rules will be followed for reporting results unless stated otherwise:

- Screen failure patients are those who signed the ICF, but never started the study treatment for any reason. For these patients, the eCRF data collected will not be included in analyses, but will be reported in the clinical study report as separate listings
- Baseline is defined as the last assessment prior to the first dose of treatment received (ie, C1D1 pre-dose)
- For Phase I, all summaries, listings, figures and analyses will be performed by treatment group
- For Phase II, all summaries, listings and figures for primary efficacy analyses and safety analyses will be presented by disease group (NSCLC, urothelial carcinoma, or synovial sarcoma)

Patients from the dose escalation and dose expansion may be pooled for the RP2D. Additional analyses not described here will also be detailed in the SAP.

Unless otherwise stated, missing data will simply be noted as missing on appropriate tables/listings.

Compliance with the protocol will be assessed by the number and proportion of patients with protocol deviations. Protocol deviations will be identified prior to database lock and will be listed and summarized.

9.2 Analysis Sets

9.2.1 Full Analysis Set

The full analysis set (FAS) comprises all patients who received at least 1 full dose or partial dose of IMCnyeso. Patients will be analyzed according to the planned treatment. The FAS will be used for all listings of raw data, demography and baseline characteristics. Unless otherwise specified, the FAS will be the default analysis set used for analyses.

9.2.2 Safety Analysis Set

The safety analysis set comprises all patients who received at least 1 full dose or partial dose of IMCnyeso. Patients will be classified in this set according to initial treatment received. The safety analysis set will be used for the safety summary of the study. If the safety analysis set and the FAS are identical, then analyses described by the safety analysis set will not be performed.

9.2.3 Per-Protocol Analysis Set

The per-protocol set (PPS) consists of a subset of FAS patients who meet these 4 criteria:

- Presence of measurable disease according to RECIST v1.1
- At least 1 post-baseline tumor assessment or discontinued prior to the first tumor assessment
- Received at least 1 dose of planned treatment at the RP2D
- No violation of key inclusion or exclusion criteria (to be defined in the SAP)

Patients in the PPS will be classified according to planned treatment. If the PPS and the FAS are identical, then analyses described by the PPS will not be performed.

9.2.4 Dose-Determining Analysis Set

The DDS consists of all patients from the safety analysis set in Phase I who meet the criteria described in [Section 6.10.2](#).

9.2.5 Pharmacokinetic Analysis Set

The PK analysis set consists of all patients who have at least 1 blood sample providing evaluable PK data. The PK analysis set will be used for all PK analyses.

Note: Patients may be removed from the estimation of certain PK parameters on an individual basis depending on the number of available blood samples. These patients will be identified at the time of analysis.

9.3 Patient Demographics and Other Baseline Characteristics

Demographic data, baseline disease characteristics, and other baseline data will be listed in detail. Qualitative data (eg, performance status) and quantitative data (eg, weight) will be summarized by descriptive statistics.

9.4 Treatment Data

Actual dose and duration in days of treatment for IMCnyeso, as well as the dose intensity (actual dose received/actual duration) and relative dose intensity (the ratio of dose intensity to planned dose/planned duration) will be summarized by descriptive statistics by treatment group.

Concomitant medications and significant non-drug therapies prior to and after the start of the study treatment will be listed by patient and summarized by anatomical therapeutic chemical term and treatment group.

The reason for discontinuation from treatment will be summarized and listed, along with dates of first and last doses, duration of exposure to each study drug, and date of discontinuation for each patient.

9.5 Primary Analysis Variables

9.5.1 Phase I: DLT

In Phase I, the primary variable is the occurrence of 1 or more DLTs. An adaptive BLRM guided by the EWOC principle will be used to guide dose recommendations and estimate the MTD, as described in [Section 6.10](#) and [Section 13.3](#).

Patients in Phase I who are ineligible for the DDS will be excluded from the primary analysis, although their data will be used for all remaining analyses.

As a supportive analysis in the Phase I dose escalation part of the study, a dose-exposure relationship may be estimated for IMCnyeso via a BLRM to further guide the dose recommendation to targeted exposure of IMCnyeso. From the estimation of the dose-exposure model, the following posterior summaries will be derived for each dose:

- Mean, median, standard deviation, and 95%-credible interval for the exposure
- The probability that the true AUC after first dose of treatment achieves the target exposure

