6.9 Starting Dose Rationale

The rationale for the QW dosing regimen in this study are based on the proof-of-concept clinical study of tebentafusp where manageable toxicity was observed with QW dosing of tebentafusp, as well as single-agent anti-tumor activity in both uveal and cutaneous melanoma.

IMCnyeso is a highly human-specific fusion protein. Neither the anti-CD3 nor the TCR portions cross react with any of the standard toxicology species, as discussed in [Section 1.3](#). Therefore, there is no relevant toxicology species to enable the setting of a starting dose using the conventional no adverse effect level (NOAEL) method. In the absence of a relevant toxicology species, MABEL, with receptor occupancy calculations, was used to set a safe starting dose. Derivation of the first clinical dose using the MABEL is shown below.

In vitro pharmacology assays measuring the efficacy of IMCnyeso against cancer cell lines were used to define the MABEL. In these assays, human T cells were added to target cells with different concentrations of IMCnyeso to determine the effects of cytokine release and killing induced at the given concentrations of IMCnyeso. The target cells used were HLA-A*02:01 positive and NY-ESO-1 positive cancer cells, which in the presence of IMCnyeso, induce the CD3 positive effector T cells in the PBMC population to both release IFN- γ and kill the tumor cells. In general, IFN- γ release is observed at IMCnyeso concentrations that are lower than the concentrations required for the observation of target-cell killing. Based on the killing assays and IFN- γ release assays, the MABEL observed in the in vitro assays for IMCnyeso is 5 pM.

The acceptable starting dose in the Phase I dose-escalation study is defined as the IV dose of IMCnyeso with a predicted C_{max} of serum at the MABEL (5 pM) and a receptor occupancy between 10%–30% at C_{max} . The use of C_{max} as the PK determinant of the starting dose prediction is based on the observed toxicity profile of the first ImmTAC in the clinic, tebentafusp, where it was observed that the related and more severe toxicities are observed in the immediate hours following dosing, when the concentration of tebentafusp was maximal. These data suggest that toxicity is related to the maximal plasma concentration more than the overall exposure or the area under the curve (AUC).

Thus, the determination of the starting dose is as follows:

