6.10.1 Intra-Patient Escalation

A recent FDA review concluded that incorporation of a step dose / IPE can result in better patient tolerance of higher doses of CD3 bispecific molecules ([Saber, 2017](#)) due to a phenomenon of induced tolerance or tachyphylaxis. IPE regimens are used for the related ImmTAC molecule tebentafusp as well as the approved CD3 bispecific blinatumomab.

If the severity of cytokine-mediated AEs tend to become less severe following the initial doses of study drug using a fixed-dose regimen, the SST may initiate a 1-step IPE regimen, in which a lower dose is given on Cycle 1 Day 1 and a higher (target) dose is given on Cycle 1 Day 8 and beyond, as shown in [Figure 6-1](#).

[figure not shown]

Figure 6-1: Schematic Illustration of a 1-Step IPE Regimen

Rules for the 1-step IPE regimen are as follows:

- The initial target dose level must be a permitted escalation step based on BLRM output and the consensus of the SST
- The initial target dose level must not exceed the fixed-dose MTD (if established)
- The C1D1 dose level must be at least one dose level below the initial target dose, and must be a dose level that has been evaluated in ≥ 3 patients using a fixed-dose regimen, with a decision to escalate based on the BLRM output and SST review of all available relevant data.
- Escalation of the target dose in subsequent cohorts may proceed as in the main dose escalation:
 - Separate MTD/RP2D may be identified using fixed-dose and 1-step IPE regimens
 - DLT will be attributed to the dose level of the most recently administered dose prior to onset of the DLT (eg, a DLT with onset on C1D4 would be attributed to the C1D1 dose level, while a DLT with onset on C1D10 would be associated to the C1D8 dose level)
- The dose level for C1D1 remains fixed for all subsequent cohorts
- Patients receiving IPE must receive the C1D1 dose prior to receiving the target dose
- If a 1-step IPE regimen is evaluated in Phase I, it may be selected for further evaluation in Phase II

Experience with other CD3 bispecific molecules (including tebentafusp and blinatumomab) indicates that multi-step IPE may mitigate the risk of a cytokine-mediated AE more effectively than a 1-step IPE or fixed-dose regimen. If further mitigation of cytokine-mediated events is desired, the SST may decide to evaluate a two-step IPE regimen, in which an intermediate dose is given on Cycle 1 Day 8, as shown in [Figure 6-2](#).

[figure not shown]

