Let d^* be the highest dose at which the DLT status of at least 3 patients is known. A dose is cleared if the ratio between it and d^* is less than or equal to 3.34. A dose is eligible if it is both cleared and the current posterior estimate of the probability that it lies in the excessive toxicity band is less than 0.25 [the EWOC rule]. The dose recommended by the N-CRM will be the eligible dose currently with the highest posterior probability of being in the target toxicity band.

Futility Rule

There will be no futility rule. Phase I cohorts will continue to enroll until either the MTD (or RP2D) is identified or the Sponsor terminates the study for other reasons.

Success Rule

The N-CRM model will recommend that enrollment to Phase I cohorts should stop once either (a) at least 6 evaluable patients have been treated in the dose range in which the MTD is currently thought to lie or (b) no dose is eligible for dosing because of the EWOC rule. The Sponsor reserves the right to continue enrollment in the Phase I cohorts beyond this time if it is considered clinically useful so to do.

Enrollment Limit

There will be no enrollment limit. Enrollment will be open.

Dose-toxicity Model

X-hats:

Let $d_i = i$ mcg, $i=1, \dots, 200$. Let \hat{x}_i denote the nominal dose used in the dose-toxicity model that corresponds to d_i . Let $d_{ref} = 0$ mcg. Then $\hat{x}_i = d_i - d_{ref} = d_i$.

Functional Form:

Let Y_j be a Bernoulli random variable indicating whether the j^{th} patient experiences a DLT ($Y_j=1$) or not ($Y_j=0$). Let \hat{x}_{ij} denote the nominal dose received by the j^{th} patient. The BLRM will model the probability that the j^{th} patient experiences a DLT as

$$p(Y_j = 1 | \hat{x}_{ij}, \alpha, \beta, \{(\hat{x}_{ik}, y_k); k = 1, \dots, j-1\}) = \frac{e^{\alpha + \beta \hat{x}_{ij}}}{1 + e^{\alpha + \beta \hat{x}_{ij}}}$$

The Prior:

The dose-toxicity model is a logistic model and takes the form:

$$\text{logit}(p) = \alpha + \beta \hat{x}$$

It is assumed that toxicity increases with increasing dose and thus the slope, β , must be greater than 0. This assumption is implemented in the model by estimating γ where $\gamma = \ln(\beta)$. The prior for α and γ takes the form

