- C1D22: pre-dose (within 2 hours), EOI (within 15 min), and 1-hour post-EOI (\pm 15 min)

Pharmacokinetics samples are to be collected at the following timepoints:

- C1D1: pre-dose (within 2 hours), EOI (within 15 min), 8-hour post-EOI (\pm 1 hr)
- C1D8 and C1D15: pre-dose (within 2 hours), EOI (within 15 min), 1-hour post-EOI (\pm 15 min), 2-hour post-EOI (\pm 15 min), 4-hour post-EOI (\pm 15 min), 6-hour post-EOI (\pm 30 min), 8-hour post-EOI (\pm 1 hr), and 12-hour post-EOI (optional, \pm 3 hr)
- C1D2, C1D9, and C1D16: 24-hour post-EOI (\pm 4 hr)
- C1D22: pre-dose (within 2 hours), EOI (within 15 min), 8-hour post dose (\pm 1 hr)

Central lab cytokine testing samples are to be collected at the following timepoints:

- C1D1: pre-dose (within 2 hours) and 4-hour post-EOI (\pm 15 min)
- C1D8 and C1D15: pre-dose (within 2 hours), 4-hour post-EOI (\pm 15 min), 8-hour post-EOI (\pm 1 hr), and 12-hour post-EOI (optional, \pm 3 hr)
- C1D2, C1D9, and C1D16: 24-hour post-EOI (\pm 4 hr)
- C1D22: pre-dose (within 2 hours) and 4-hour post-EOI (\pm 15 min)
- Additional samples may be collected if a patient has suspected CRS. Recommended timepoints are within 5 hours and 1 week after onset of CRS.

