3.4 Dose Adjustment/Modifications

All doses administered to subsequent cohorts of patients will be determined by the SST and will be guided by the BLRM and will be subject to both the EWOC principle and the escalation rule. Dose-escalation decisions will be made by the SST, which will consist of the Study Investigators, the Sponsor Medical Monitor, and a Statistician. For each cohort, dose escalation or de-escalation decisions will be based on the SST's review of all relevant data available, from all dose levels evaluated in the ongoing study, including safety information, DLTs, all \geq Grade 2 toxicity data, PK, and pharmacodynamic data from evaluable patients (as defined in Section 6.10.2 of protocol version 4.0). The data and BLRM dose recommendations will be discussed and agreed upon during the dose-escalation teleconference (DETC), and all decisions will be documented in the meeting minutes and shared with all participating Principal Investigators.

The actual dose levels that have been tested in this study are shown in **Table 1** below. Actual doses will be determined using the BLRM and must be agreed upon by the SST.

Table 1 - IMCnyeso Dose Levels for Phase I Dose Escalation

Cohort number	Cohort description	IMCnyeso Dose(s) Tested	Enrollment (n)
1	3 mcg fixed dose	3 mcg	4
2	10 mcg fixed dose	10 mcg	3
3	30 mcg fixed dose	30 mcg	5
4	100 mcg fixed dose	100 mcg	3
5	30-100 mcg intra-patient dose escalation	30-100 mcg	5
6	30-100-180 mcg intra-patient dose escalation	30-100-180 mcg	4
7	30-100-300 mcg intra-patient dose escalation	30-100-300 mcg	6 (planned)

To better understand the safety, tolerability, and PK profile of single agent IMCnyeso, additional cohorts of patients may be enrolled at preceding dose levels or intermediate dose levels, before or in parallel, while proceeding with further dose escalation. The outcome from these cohorts will be included in the BLRM.

If the first 2 patients in a previously untested dose level experience a DLT, additional enrollment in that cohort will stop, the BLRM will be updated with this new information, and the SST will evaluate the available safety, PK, and pharmacodynamic data. By incorporating information gained at the preceding dose levels and provided the BLRM predicts that the risk of excessive toxicity remains below 25% (EWOC), additional patients may be enrolled at this dose level or a lower dose level as agreed upon by the SST.

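### Protocol 9.5.1: the optional dose-exposure analysis is indexed to first-dose AUC, which is the 30 mcg lead-in in every step-up cohort, and names a model type that the documents define only for DLTs

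*Protocol*

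**What the plan says.** Protocol 9.5.1, after the primary DLT analysis, adds a supportive one: "a dose-exposure relationship may be estimated for IMCnyeso via a BLRM to further guide the dose recommendation to targeted exposure of IMCnyeso". Two posterior summaries are promised for each dose. The first is "Mean, median, standard deviation, and 95%-credible interval for the exposure". The second is "The probability that the true AUC after first dose of treatment achieves the target exposure". The documents give no value for the target exposure.

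The only BLRM with a stated likelihood is in Protocol 13.3.1. There the outcome is a Bernoulli DLT indicator: "The dose-toxicity model is a logistic model and takes the form" logit(p) = α + β·dose.

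Under Protocol 6.10.1, in a 1-step IPE regimen "a lower dose is given on Cycle 1 Day 1 and a higher (target) dose is given" from C1D8. In a 2-step regimen the target dose comes only after the C1D1 and C1D8 doses, that is, from C1D15. SAP Table 1 has three such cohorts, the last described as "30-100-300 mcg intra-patient dose escalation".

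The IPE sampling schedule in Protocol 13.4 takes three PK samples on C1D1. The longer series is on later days: "C1D8 and C1D15: pre-dose (within 2 hours), EOI (within 15 min), 1-hour post-EOI" and onward to 8 hours, with an optional 12-hour sample. SAP 10.1 derives Cmax on all three days, AUClast on C1D1, and AUCtau on C1D8 and C1D15.

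**The concern.** Other parts of the protocol were adapted to IPE. DLTs are attributed to the most recent dose (6.10.1), PK sampling was shifted to the days when higher doses are given (13.4), and a separate dose-toxicity model is foreseen for IPE target doses above 150 mcg (13.3.1). The exposure probability in 9.5.1 still refers to the first dose. For IPE patients that is the lead-in, not the dose about which a recommendation is needed.

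The named model is a second gap. A logistic model for a yes/no outcome returns a probability. It has no parameter for the mean or spread of AUC, so the first promised summary cannot come from it.

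If the analysis were run as written, its statement about reaching a target exposure at 180 or 300 mcg would rest on extrapolation from lower doses, although measurements at those doses would be in the database.

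**Working it through.** Section 9.5.1 states no sample size, precision or error rate, so there is no plan figure to reproduce. The check tabulates which doses each indexing rule observes and compares their precision.

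**Inputs (SAP Table 1; days from Protocol 6.10.1)**

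| Cohort | n | First dose (mcg) | Target dose (mcg) | Target first given |
|---|---|---|---|---|
| 1 | 4 | 3 | 3 | C1D1 |
| 2 | 3 | 10 | 10 | C1D1 |
| 3 | 5 | 30 | 30 | C1D1 |
| 4 | 3 | 100 | 100 | C1D1 |
| 5 | 5 | 30 | 100 | C1D8 |
| 6 | 4 | 30 | 180 | C1D15 |
| 7 | 6 (planned) | 30 | 300 | C1D15 |

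- First doses: 3 mcg (4), 10 (3), 30 (5 + 15 = 20), 100 (3); none at 180 or 300. Total 30.
- Target doses: 3 (4), 10 (3), 30 (5), 100 (3 + 5 = 8), 180 (4), 300 (6). Total 30.
- Lead-in as a share of target: 30/100 = 30%, 30/180 = 16.7%, 30/300 = 10%.
- Reach beyond the highest first dose: 180/100 = 1.8-fold, 300/100 = 3-fold.
- IPE first doses alone contain a single dose level, so they identify no slope. The slope has to come from the fixed-dose cohorts.

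**Precision in units of the residual SD.** Take the Power Model of Protocol 9.6.3 with a common intercept and one record per patient: ln(exposure) = a + b·ln(dose) + error, SD s. Then SE(b) = s/√Sxx, and the SE of mean log exposure at dose d is s·√(1/n + (ln d − x̄)²/Sxx), where x = ln(dose).

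| Records used | n | x̄ | Sxx | SE(b) | SE at 180 mcg | SE at 300 mcg |
|---|---|---|---|---|---|---|
| First dose | 30 | 3.105 | 26.54 | 0.194s | 0.445s | 0.537s |
| Target dose | 30 | 4.005 | 70.15 | 0.119s | 0.231s | 0.273s |

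At 300 mcg, ln 300 = 5.704:

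- First dose: √(1/30 + 2.599²/26.54) = √(0.0333 + 0.2545) = 0.537.
- Target dose: √(1/30 + 1.699²/70.15) = √(0.0333 + 0.0412) = 0.273.
- Reduction: 1 − 0.273/0.537 = 49%.

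**On the exposure scale.** The documents give no between-patient CV, so 30%, 50% and 70% are assumed, with s = √ln(1 + CV²) = 0.294, 0.472 and 0.631. The 95% uncertainty factor on typical AUC is exp(t·SE), with t = 2.048 on 28 df, or 2.017 on 43 df for the 45-record row (30 first-dose plus 15 IPE target-dose records). That row treats repeat records from one patient as independent, which is a simplification.

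| Records used | 180 mcg (CV 30 / 50 / 70%) | 300 mcg (CV 30 / 50 / 70%) |
|---|---|---|
| First dose only, 30 | 1.31 / 1.54 / 1.78 | 1.38 / 1.68 / 2.00 |
| Target dose only, 30 | 1.15 / 1.25 / 1.35 | 1.18 / 1.30 / 1.42 |
| First plus IPE target, 45 | 1.14 / 1.23 / 1.32 | 1.17 / 1.29 / 1.40 |

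**What the standard errors leave out.** They assume one slope throughout. If the slope above 100 mcg were 0.8 or 1.2 instead of 1, exposure at 300 mcg would differ by 3^(−0.2) = 0.80-fold or 3^(0.2) = 1.25-fold. First-dose data stop at 100 mcg and could not show this. The kinetic linearity cited in Protocol 6.9 is from mice.

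**The case against.** The strongest reply is that little depends on this analysis. It is optional and supportive. Dosing is guided primarily by the DLT model with overdose control, and the Study Safety Team also reviews PK. The SAP neither describes the analysis nor lists an output for it. All of this stands, and it is why the point is minor.

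A reader might also infer more than the documents support:

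- *Exposure is run through the DLT model.* The protocol says only that a BLRM is used. Reuse of the DLT logistic is an inference from its being the only one specified. The supportable statement is that no likelihood for a continuous exposure is given.
- *The 180 and 300 mcg doses never enter.* Only the second summary is tied to the first dose. The first concerns exposure at each dose, and nothing bars C1D8 or C1D15 data from the fit.
- *The analysis says almost nothing about target doses.* Fixed-dose cohorts have full C1D1 profiles up to 100 mcg, which is cohort 5's target. Only 180 and 300 mcg need extrapolation.
- *The metric is AUC only, against the protocol's own view.* AUC appears only in the second summary. The statement that "toxicity is related to the maximal plasma concentration more than the overall exposure" concerns tebentafusp and supports the starting dose. It is a reason to add Cmax, not a contradiction.
- *Target-dose PK goes unused.* SAP 10.1 summarises Cmax and AUCtau on C1D8 and C1D15 by cohort and dose.

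What survives is narrow. The only exposure probability the section promises is indexed to the wrong administration for IPE, and the model it names is not specified for exposure.

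**Conclusion.** The point holds as a minor one: 9.5.1 is wrong as written for IPE regimens. First-dose AUC is lead-in AUC in 15 of 30 patients (6 of them planned), and no patient receives 180 or 300 mcg first. Indexing to the target dose turns two extrapolated doses into observed ones and cuts the SE of mean log exposure at 300 mcg by 49%. At an assumed CV of 50%, the 95% factor there falls from 1.68 to 1.30 with target-dose records only. These figures rest on a log-log model with constant residual SD and a common intercept, and on cohort 7 enrolling its planned 6. The MTD rule, sample size and error rates do not change, and nothing here shows that any dosing decision was affected.

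**What to change.** In Protocol 9.5.1:

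1. Replace the reference to a BLRM with a Bayesian log-linear regression of ln(exposure) on ln(dose administered), the Power Model form of 9.6.3.
2. State which records enter. Either use all Cycle 1 profiles, lead-in and target, each indexed to the dose actually given, with a patient random intercept; or use one target-dose record per patient with a common intercept. A patient-specific intercept cannot be separated from residual error with one record per patient, so the two should not be mixed.
3. Index the probability to AUC, and Cmax, after the first administration at the target dose: C1D1 for fixed dose, C1D8 for 1-step and C1D15 for 2-step IPE.
4. Use one AUC definition or window on all three days, since the SAP now has AUClast on C1D1 and AUCtau on the others.
5. Define the target exposure.

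Then carry the analysis into SAP 10.1. If it is no longer intended, say so in SAP section 12, which at present reports no substantial change from the protocol.

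The cost is wording and a small model. No new samples are needed, because the target-dose profiles are already scheduled.
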